The purpose of this 8-week phase will be to assess the effect of JUUL on product uptake and use, smoking behavior, and nicotine dependence, as well as level of toxicant exposure.. During this phase, participants will receive three OKHL coaching calls (0, +14 days, +4 weeks), complete EMAs twice a day (~120 EMAs over the phase), and complete two follow-up full assessment battery calls (0 and +8 weeks). Participants randomized to JUUL will be provided EC education, behavioral counseling, and asked to attempt to completely switch to the product for the next 8 weeks. Those randomized to NRT will be provided OKHL smoking cessation counseling and provided 8 weeks of NRT. All products to which participants will be randomized, will be provided at no cost and will be mailed to them. New cartridges will be provided based on estimated use given cigarettes per day. (see Table 2 for measures collection schedule).

Surveillance Phase

The purpose of this 4-week period is to assess how EC use evolves over time; specifically, continued use as measured by reported purchase of commercial EC product, transitions to other types or styles of ECs, smoking and other tobacco use behavior and patterns, as well as continued monitoring of iCO, a biomarker of toxicant exposure, and health effects over the 4-week period. During this phase, participants will continue to complete daily EMAs (~60) and a follow-up full assessment battery call at +12 weeks. Participants will be sent saliva collection kits if iCO is unable to be completed. Participants will not be provided ECs or NRT during this phase, but use of ECs, NRT, and other tobacco products will continue to be tracked. Also, this phase will help us to continue to track any adverse events that may occur following use of the JUUL and NRT. Those continuing to use any tobacco or EC product at the end of the surveillance phase will be advised that they can contact their state quitline and/or other local smoking cessation resources.

JUUL Education and Counseling

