days after the emergency occurs. Except in emergency situations, prior approval will be obtained from the sponsor and IRB for any protocol change necessary to reduce risk for subjects or data quality and if the change may affect the scientific soundness of the plan or the rights, safety, or welfare of subjects, prior FDA, NIDA, and IRB approvals will be obtained as required by 21 CFR 812.150.

- Any use of the device *without obtaining informed consent* will be submitted within 5 working days after such use.
- A *final report* will be submitted within 3 months following termination or completion of the investigation or the investigator's part of the investigation. These will include Annual Progress Reports and Final Reports.
- *Any further information* requested by FDA or the IRB about any aspect of the investigation.
- *Withdrawal of IRB approval* of the investigator's part of the investigation will be reported to only the Sponsor within 5 working days of such action.
- *All changes to the protocol or DSMP (other than staffing changes)* will require approval by the NIDA Program Officer prior to implementation.
- *Serious Adverse Events* must be reported to NIDA within 72 hours.
- A *DSM report* will be sent to NIDA annually with contents to include:
 - Brief description of the trial
 - Baseline sociodemographic characteristics
 - Retention and disposition of study participants
 - Quality assurance Issues
 - Regulatory issues
 - Adverse event listing
 - Severe adverse event descriptions

Conflicts of Interest: There are no conflicts of interest to report.

3. Measures

All measures, including EMAs and iCO, have been used previously by [name] and his team. iCO, a biomarker of health and exposure, was chosen because it has shown reasonable laboratory reproducibility, has clear differences in levels between smokers and nonsmokers, demonstrate a dose-response relationship, and/or decrease upon tobacco cessation^{108,109}.

Questionnaire data will be collected over the phone or in-person by a trained research assistant and data will be entered into a secured and encrypted database using REDCap. See Table 2 for timing of measures.

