The research protocol calls for current smokers who recently failed to quit smoking using the standard QL program, to attempt to completely substitute JUUL or NRT. E-cigarettes are no more harmful than conventional cigarettes, and there is some evidence that that may offer reduced harm. Questionnaires and the exhaled breath collection procedure is non-invasive and involves minimal risk to study participants. Potential risks are as follows: a) risk of using NRT, b) risk of using e-cigarettes, c) dual use of cigarettes and e-cigarettes, d) loss of confidentiality or privacy, e) potential for undermining smoking cessation, and f) lack of appropriate storage of nicotine-containing products in a house with children and pets.

7. Protections Against Risk

Efforts to reduce risk are as follows:

a) Risk of using the NRT: The risk of side effects and adverse events is very low. These products are FDA-approved for smoking cessation, and sold at convenience stores nationwide, without a prescription. Nevertheless, participants will be screened for general medical precautions (pregnancy, cardiovascular disease), and all participants will be monitored for adverse events during the study period. Study personnel will assess for adverse events via self-report at all follow-up visits. Smokers will also be provided a study smartphone with a direct line to report an adverse event between follow-up visits. Any Serious Adverse Events will be reported to the study's medical monitor and then to the OSU IRB and to NIDA. We will withdraw participants who have a Serious Adverse Event, or become pregnant or begin to breastfeed. The most likely adverse event (potential for nicotine overdose) is anticipated to be rare (<5% in our team's previous studies) and mild (nausea, headache, disrupted sleep), and will be handled quickly (i.e., advice to participant to reduce or stop NRT use).

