All Serious Adverse Events regardless of study product group or suspected relationship to Study Medication must be reported immediately to the medical monitor then to IRB and then to NIDA. A Serious Adverse Event is any adverse study product experience occurring at any dose that: (1) results in death; (2) is life-threatening; (3) results in inpatient hospitalization or prolongation of existing hospitalization; (4) results in a persistent or significant disability/incapacity; or (5) results in congenital anomaly/birth defect. Important medical events that may not result in death, be life-threatening, or require hospitalization may be considered Serious Adverse Events when, based upon appropriate medical judgment, they may jeopardize the patient/subject and may require medical or surgical intervention to prevent one of the outcomes listed in this definition. Any Serious Adverse Event or death must be reported immediately independent of the circumstances or suspected cause if it occurs or comes to the attention of the principal investigator at any time during the study through the last follow-up visit required by the protocol or 30 days after the last administration of Study Product, whichever comes later. Any Serious Adverse Event occurring at any other time after completion of the study must be promptly reported if a causal relationship to Study Product is suspected. The only exception to these reporting requirements is Serious Adverse Events that occur during a period in which no study product is administered. For all Serious Adverse Events, the investigator is obligated to pursue and provide information as requested by the OSU IRB in addition to that on the Adverse Event Form. In general, this will include a description of the adverse event in sufficient detail to allow for a complete medical assessment of the case and independent determination of possible causality. Information on other possible causes of the event, including concomitant medications and illnesses, must be provided. The PI will ensure that information is reported immediately and

Switching to a Vaping Device: Evaluating Risk Reduction among Quitline Treatment Failures

information entered in the Adverse Event Form are accurate and consistent. Event will be reported by online portal for NIDA (<https://saetrs.nida.nih.gov/saetrs/view/index.cfm>) and FDA (<https://www.safetyreporting.hhs.gov/srp2/default.aspx?sid=316ef188-4fb7-4100-968f-c6a6c72058d0>), by telephone, or other means.

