Preventing and Limiting Adverse Events

We will monitor for risk of using e-cigarettes and NRT by screening participants for general medical precautions. The most likely adverse event (potential for nicotine overdose) is anticipated to be rare and mild based on the PI's previous studies, and will be handled quickly (i.e., advice to participant to reduce or eliminate nicotine use). Lab studies of toxin exposure suggest that e-cigarettes incur no greater risk to health than do combustible cigarettes. The PI and study personnel will be available for any questions that participants may have about e-cigarettes, NRT, smoking, or smoking cessation. Participants will be provided a study phone and data plan at no cost, to contact study personnel at any time. Any adverse events, breaks of confidentiality, or any other data or safety issues that arise will be discussed immediately between study personnel and the PI.

Collection of Adverse Events

The collection of adverse events will be on a self-report basis and logged within an electronic data capture system (REDCap) or collected using standardized paper forms and will only be identified with the study's ID of the participant.

Adverse Event Reporting Timelines

- All intervention staff are required to notify the PI of any Serious Adverse Events immediately.
- All Serious Adverse Events will be reported immediately to the medical monitor who will determine their severity and appropriate action or response.
- In accordance with current standard procedure, the PI will notify the OSU IRB of all Serious Adverse Events within 24 hours.
- In accordance with new policy and procedure, the PI will notify the National Institutes of Drug Abuse of all Serious Adverse Events within 72 hours.
- All Non-serious AEs will be reviewed weekly by the medical monitor or PI, for categorization and possible action.

Switching to a Vaping Device: Evaluating Risk Reduction among Quitline Treatment Failures

I. Literature Cited

1. CDC. Vital Signs: Current Cigarette Smoking Among Adults Aged \geq 18 Years—United States, 2005–2010. In: MMWR, ed.2011.
2. Treating tobacco use and dependence: 2008 update. Clinical Practice Guidline. 2008. at [http://www.ahrq.gov/clinic/tobacco/treating_tobacco_use08.pdf.'\).](http://www.ahrq.gov/clinic/tobacco/treating_tobacco_use08.pdf.)

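### The SAE reporting exception for time off product cancels the plan's own post-product reporting window, and NRT falls outside the definition of Study Product

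*Combined protocol and SAP*

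**What the plan says.** All references are to the combined protocol and SAP.

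**SAE window (H.2, Serious Adverse Events).** Any SAE or death, whatever its cause and in either arm, must be reported at once "through the last follow-up visit required by the protocol or 30 days after the last administration of Study Product, whichever comes later". After that, an SAE "occurring at any other time after completion of the study must be promptly reported if a causal relationship to Study Product is suspected".

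**Exception (same section, next sentence).** "The only exception to these reporting requirements is Serious Adverse Events that occur during a period in which no study product is administered". It has no time limit and no stated reason. Neither the period nor administration is defined, although the products are mailed and self-used.

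**Product-free phase (D.1 Design Overview; D.2 Surveillance Phase).** Product is supplied for 8 weeks. For weeks 9-12, "Participants will not be provided ECs or NRT during this phase". D.2 says this phase will also help the team to "continue to track any adverse events that may occur following use of the JUUL and NRT".

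**Reporting rules elsewhere, none with an exception.**
- H.2, Adverse Event Reporting Timelines: "the PI will notify the OSU IRB of all Serious Adverse Events within 24 hours". The same list sends all SAEs to the medical monitor at once and to NIDA within 72 hours.
- D.2, Regulatory Issues: SAEs "must be reported to NIDA within 72 hours".
- G.7, items a) NRT and b) e-cigarettes: any SAE goes to the "medical monitor and then to the OSU IRB and to NIDA".

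**Definition (H.2, opening paragraph).** Study Product, capitalised, means e-cigarettes. The causality assessment names Study Product or another illness as the options. The Serious Adverse Events text also uses lower-case study product and an undefined term, Study Medication.

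**The concern.** The exception does not carve a small piece out of the rule. It removes the part of the rule written for time after product use. A coordinator who learns in week 10 that a participant who has stopped using product was hospitalised can file nothing, citing the exception. A second coordinator can report the same event to the medical monitor, IRB and NIDA, citing the timelines list. Both are following the protocol, and no text says which rule prevails.

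The section's own SAE definition gives a concrete case: it lists birth defects. Pregnancy at entry is an exclusion, a participant who becomes pregnant is withdrawn, and supply lasts 8 weeks. A defect found at delivery would therefore normally fall in a product-free period, where the exception applies.

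Separately, NRT is a randomised product with its own risk section, yet an NRT-related SAE has no named place in the causality wording.

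What is at stake is SAE reporting and attribution. Collection is not affected: H.2 records adverse events in both arms, and Table 2 schedules them at weeks 8 and 12.

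**Working it through.** The plan gives no figure of its own here, so the check is a comparison of texts plus day counts.

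**Inputs.** 8-week product phase and 4-week surveillance phase (D.1); last follow-up at week 12 (D.2); 420 randomised and 20% attrition (E.1); the 30-day clause (H.2).

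**1. Timeline.** Supply ends on day 8 × 7 = 56. Last follow-up is day 12 × 7 = 84.

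**2. Window without the exception.** Assuming last use on day 56, the 30-day limit is 56 + 30 = day 86. The later of 84 and 86 is day 86.

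**3. Effect of the exception on the 30-day clause.** That clause covers only days after last administration. Whatever the date of last use, all 30 are days without administration, so 30 − 30 = 0 remain. The post-study clause is emptied in the same way once use has stopped.

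**4. Overlap.** With last use on day 56, days 57-84 (28 of the 30) are also weeks 9-12, which the follow-up-visit limb already covers. Only days 85-86 rest on the 30-day limb alone. The 30 days and the week 9-12 share below should not be added together.

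**5. Share of follow-up in weeks 9-12,** assuming everyone's use stops when supply ends:
- No dropout: 420 × 4 = 1,680 of 420 × 12 = 5,040 person-weeks, or 33.3%.
- 20% attrition, all at week 8: 420 × 0.8 = 336 remain. Then 336 × 4 = 1,344 of 420 × 8 + 1,344 = 4,704, or 28.6%.

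Use of leftover product in weeks 9-12 lowers both figures. Stopping before day 56 adds earlier product-free time. As an extreme illustration, if everyone stopped at week 4, 420 × 8 = 3,360 of 5,040 (67%) would be open to the exception.

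**6. The texts applied to one event:** an SAE in week 10, participant no longer using product.

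| Text | Result |
|---|---|
| H.2 SAE window | Report |
| H.2 exception | Exempt |
| H.2 timelines list | Report |
| D.2 Regulatory Issues | Report |
| G.7 a) and b) | Report |

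**7. NRT clock.** No Study Product, as defined, is administered in the NRT arm, so its window ends at day 84. Against a clock that counted NRT, the loss is (last use + 30) − 84, with a floor of zero:
- last use by day 54: 0 days;
- last use on day 56: 2 days;
- last use on day 70 (assumed leftover use): 16 days.

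**The case against.** The strongest objection is that the exception may have been meant narrowly, for example for the time between consent and arrival of the mailed product. That is possible, but the sentence does not say so, and it follows directly on the clauses about time after last use. Limiting the sentence would accommodate that intent.

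A second objection is that the rules in D.2 and G.7 are summaries, and a detailed section may carry an exception that summaries do not repeat. This has some force, and those texts are weaker support. It does not help with the conflict inside the Serious Adverse Events text or with the surveillance phase's stated purpose. The timelines list is itself part of H.2 and speaks of all SAEs. If the exception is confined to its own subsection so that the timelines still apply, staff are left with two opposite instructions.

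Third, person-weeks do not count missed SAEs. That stands.

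Fourth, the NRT gap is small. H.2 asks for information on other possible causes, including concomitant medication, so NRT could be written in; SAEs are reportable in both arms; and G.7 a) covers NRT. This also stands. The NRT point is secondary and concerns attribution and timing. One caution remains: if lower-case study product in the exception were read as e-cigarettes only, it could be taken to exempt the whole NRT arm, contrary to the all-arm rule in the same section.

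**Conclusion.** The concern holds. As written, the exception contradicts the reporting window in the same section, the stated purpose of the surveillance phase, and the SAE rules elsewhere that carry no exception.

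- The loss of all 30 days of the 30-day clause follows from reading the exception as worded, and needs no assumption about when use stops.
- The 33% (or 29%) share is an upper bound for weeks 9-12 only, and assumes use ends with supply.
- The number of SAEs affected cannot be stated.
- For NRT, the clock loss is about 2 days under the planned schedule, together with the post-study causality clause and the causality wording. The NRT arm remains covered through the week-12 visit.

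This should be corrected: it is a conflict in safety reporting, while collection of adverse events is intact.

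**What to change.** 1. In H.2 (Serious Adverse Events), delete the exception, or limit it expressly so that it cannot override the window and post-study clause in the same section. If a narrow period such as time before product arrives was meant, say so. Reconcile the result with D.2 (Surveillance Phase, Regulatory Issues), G.7 a) and b), and the H.2 timelines list.
2. In the opening paragraph of H.2, define Study Product as both randomised products, JUUL and NRT, for causality, the 30-day clock and SAE reporting. Use that one term throughout in place of the present mix.

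**Cost.** Two or three sentences. D.2 (Regulatory Issues) requires NIDA Program Officer approval for changes to the protocol or the monitoring plan. It also calls for prior sponsor and IRB approval of changes needed to reduce risk, and for FDA approval as required where safety may be affected. A few more SAE reports may be filed. Sample size, visits and data collection do not change.
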